### 3.2. Secondary Endpoints

### **Key Secondary Efficacy Endpoints Subject to Alpha Control:**

- Extent of disease control defined as the number of cumulative weeks over the planned 24-week treatment period with platelet counts of  $\geq 50 \times 10^9 / L$  in the chronic ITP population.
- Proportion of patients in the overall population (chronic and persistent ITP) with a sustained platelet count response defined as achieving platelet counts of at least 50×10^9/L for at least 4 of the 6 visits between week 19 and 24 of the trial.
- Incidence and severity of the WHO-classified bleeding events in the overall population.
- Proportion of patients in the overall population achieving platelet counts of at least  $50 \times 10^9$ /L for at least 6 of the 8 visits between week 17 and 24 of the trial.

### Other Secondary Endpoints Not Subject to Alpha Control:

- Percentage of patients with overall platelet response defined as achieving a platelet count of  $\geq 50 \times 10^9$ /L on at least 4 occasions at any time during the 24-week treatment period.
- Extent of disease control defined as the number of cumulative weeks until week 12, with platelet counts of  $\geq 50 \times 10^9$ /L.
- Percentage of patients with overall platelet response defined as achieving a platelet count of  $\geq 50 \times 10^9$ /L on at least 4 occasions at any time until week 12.
- Mean change from baseline in platelet count at each visit.
- Time to response defined as the time to achieve 2 consecutive platelet counts of  $\geq 50 \times 10^9 / L$ .
- Rate of receipt of rescue therapy (rescue per patient per month).

argenx BVBA Confidential Page 41 of 162

- Proportion of patients for whom dose and/or frequency of concurrent ITP therapies have increased at week 12 or later.
- The number of cumulative weeks over the planned 24-week treatment period with platelet counts  $\ge 30 \times 10^9$ /L and at least  $20 \times 10^9$ /L above baseline.
- In patients with baseline platelet count of  $<15\times10^9/L$ , the number of cumulative weeks over the planned 24-week treatment period with platelet counts of  $\ge 30\times10^9/L$  and at least  $20\times10^9/L$  above baseline.
- Change from baseline in PRO (FACIT-Fatigue, Fact-Th6) and QoL (SF-36) at planned visits.
- Incidence of anti-drug antibodies (ADA) to efgartigimod.
- Pharmacokinetic parameters of efgartigimod: maximum observed serum concentration (Cmax) and serum concentration observed predose (Ctrough).
- Pharmacodynamics markers: Total IgG, IgG isotypes (IgG1, IgG2, IgG3, IgG4), antiplatelet antibody levels.

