# 2.2. Secondary Objectives

- To evaluate the efficacy of efgartigimod compared to placebo in overall platelet count response.
- To evaluate the safety and tolerability of efgartigimod administered IV weekly or q2w.
- To evaluate the incidence and severity of bleeding events while receiving treatment with efgartigimod compared to placebo.
- To evaluate the use of rescue treatment and changes in concurrent ITP therapy while receiving treatment with efgartigimod compared to placebo.
- To evaluate the effects of efgartigimod treatment on QoL measures and PRO compared to placebo.
- To assess the immunogenicity of efgartigimod.
- To assess the PK of efgartigimod.
- To assess the PD effects of efgartigimod.

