# Medical Care of Patients After End-of-Treatment or Early Discontinuation

After a patient has completed the trial, has withdrawn/discontinued early, or does not roll over to the open-label extension trial (ARGX-113-1803) usual treatment will be administered if required, in accordance with the trial site's standard of care and generally accepted medical practice depending on the patient's individual needs.

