3.5.2 Derivation rules

Based on their start and stop date, therapies will be allocated into 1 or both of the following categories:

- Prior: any therapy that strictly started before the first IMP dose date.
- Concomitant: any therapy that was taken on or after the first IMP dose date.

A medication that started before the first IMP dose date and continued during the study will be classified as both prior and concomitant.

SGS	Statistical Analysis Plan	
ARGX-113-1801	Final analysis	Final 1.0 of 28MAR2022

The ITP-specific therapies will be allocated to the following categories:

- Prior ITP therapy: stopped prior to first IMP dose date
- Continued concurrent ITP therapy: started prior to first IMP dose date and continued after first IMP dose date
- New concurrent ITP therapy: started after first IMP dose date

Therapies with (partially) missing dates will be allocated to each category unless the available parts of the therapy start or stop date or the started prior to trial/ongoing at end of trial flag provide evidence not to do so.

Type of ITP therapy:

- Corticosteroids: selection based on ATC2 = 'H02'
- IVIG, anti-D: selection based on ATC2 = 'J06' or CMDECOD = 'ANTI-D IMMUNOGLOBULIN'
- Thrombopoietin-receptor agonists (TPO-RA): selection based on CMDECOD = ('AVATROMBOPAG MALEATE' or 'AVATROMBOPAG' or 'ELTROMBOPAG' or 'ELTROMBOPAG OLAMINE' or 'ROMIPLOSTIM')
- Fostamatinib: selection based on CMDECOD = ('FOSTAMATINIB' or 'FOSTAMATINIB DISODIUM')
- Other immunosuppressants (azathioprine, cyclophosphamide, cyclosporine A, mophetil mycophenolate, vinca alkaloids): selection based on CMDECOD = ('AZATHIOPRINE' or 'CICLOSPORINE' or 'CYCLOPHOSPHAMIDE' or 'MYCOPHENOLATE MOFETIL' or 'MYCOPHENOLATE SODIUM' or 'SIROLIMUS' or 'VINBLASTINE SULFATE' or 'VINCRISTINE' or 'VINCRISTINE SULFATE')
- Danazol: selection based on ATC4 = 'G03XA'
- Dapsone: selection based on ATC4 = 'J04BA'
- Anti-CD20 (Rituximab): selection based on ATC4 = 'L01XC'
- Other: ITP therapies that are not in any of the previous 9 categories

Rescue ITP therapy will be allocated to the following categories:

- methylprednisolone, dexamethasone, prednisone: selection based on ATC4
 = "H02AB"
- immunoglobulins given IV (IVIg): selection based on ATC4 = "J06BA"
- IV anti-D: selection based on CMDECOD = 'ANTI-D IMMUNOGLOBULIN'
- platelet transfusions: selection based on CMDECOD = 'PLATELETS, CONCENTRATED'
- other: rescue medications that are not in any of the 4 previous categories

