c) SF-36 (v2.0): The SF-36 is a 36-item scale constructed to survey healthrelated QoL on 8 domains: limitations in physical activities due to health problems; limitations in social activities due to physical or emotional problems; limitations in usual role activities due to physical health problems; bodily pain; general mental health (psychological distress and well-being); limitations in usual role activities due to emotional problems; vitality (energy and fatigue); and general health perceptions. SF-36 scores for the 8 subdomains, and norm-based physical and mental component summaries scores (P-CS and M-CS) will be calculated using a dedicated software: QualityMetric Health OutcomesTM Scoring Software 5.1. 2009 US population norm is used. Missing values are handled in the software: Scale scores can be computed if at least one item in the scale is answered. The Physical Component Summary (P-CS) score can be calculated when seven scale scores are available, and the Physical Functioning (PF) scale is not missing. The Mental Component Summary (M-CS) score can be calculated when at least seven scale scores are available, and the mental Health (MH) scale is not missing. QualityMetric's Missing Data Estimation chooses a unique scoring algorithm to apply to the calculation of the summary scores depending upon which particular scale score is missing from the eight scale profiles¹¹. More details on the calculation of SF-36 scores can be found in the OPTUM[®] PRO CoRE manual.

Missing scores will only be imputed for the Mixed Model for Repeated Measurements (MMRM). See section 4.1.3.6

6) Rate of receipt of rescue therapy: number of times rescue therapy is given per month, calculated as $\frac{\text{Total number of occurences}}{\text{total days in treatment phase}} \times 30.4$

Occurrence: a period of maximum 5 days where 1 or more rescue treatments are administered simultaneously or consecutively to the study patient. The start date/time of the occurrence is the start of the administration of the first rescue treatment. If this period exceeds the maximum of 5 days, a new occurrence will be assigned, with start date/time of the occurrence being the start date 5 days after the initial occurrence start date.

7) Proportion of patients for whom dose and/or frequency of concurrent ITP therapies have increased at week 12 or later.

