Derivation: a patient is counted if (start date concurrent ITP therapy \geq target ADY of analysis visit corresponding to week 12) AND (dose > previous dose of the specific ITP therapy OR frequency > previous frequency of the specific ITP therapy OR new ITP therapy).

SGS	Statistical Analysis Plan	
ARGX-113-1801	Final analysis	Final 1.0 of 28MAR2022

8) Time to platelet count response defined as the time to achieve 2 consecutive platelet counts of $\geq 50 \times 10^9$ /L.

Derivation: It will be calculated as the difference between the first assessment date at which the condition '2 consecutive platelet counts $\geq 50 \times 10^9/L$ ' is fulfilled, taking into account all platelet count measurements (also the unscheduled ones), and first IMP intake date.

Time to platelet count response (days) = date (first assessment) – first IMP date + 1:

Response Situation	Time to Platelet Count Response	Outcome
No occurrence of platelet count of $\ge 50 \times 10^9/L$	Date of last available platelet count ^{***} – first IMP date ^{**} + 1	Censored
Early discontinuation of treatment (prior to W24) due to lack of efficacy or due to AE [*]	Early discontinuation date – first IMP date ^{**} + 1	Censored
Dose and/or frequency of concurrent ITP therapy increased*	Concurrent ITP therapy start date – first IMP date ^{**} + 1	Censored
Platelet count response	Date (first assessment) – first IMP date ^{**} + 1	Event

Table 5: Definition for Time to Platelet Count

* only applicable if the event (reaching platelet count response) has not occurred before

** or date of randomization for subjects not treated

*** or date of last contact for subject with no platelet count assessments

In case of rescue therapy, the platelet count cannot be used for 4 weeks after the initiation of the therapy (the initiation of the therapy is the start date/time of the administration of the first rescue treatment for that occurrence). The platelet count will be interpreted as $<50 \times 10^{9}$ /L for the 4 analysis visits following the initiation of the rescue therapy. Missing values not due to one of the main intercurrent events will be handled as described in section 4.1.2.5 (approach 1).

- 9) Extent of disease control defined as number of cumulative weeks over the planned 24-week treatment period with platelet counts:
 - a) $\geq 30 \times 109/L$ and at least 20×109/L greater than the baseline value

SGS	Statistical Analysis Plan	
ARGX-113-1801	Final analysis	Final 1.0 of 28MAR2022

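### SAP 4.1.2.3 item 7 counts increases and new starts of ITP therapy from week 12 with no end date, so therapy begun in the off-drug follow-up is included, and only for patients who do not roll over or who leave the trial early

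*Protocol*

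**What the plan says.** Protocol 3.2 lists, among the secondary endpoints without alpha control, the "Proportion of patients for whom dose and/or frequency of concurrent ITP therapies have increased at week 12 or later". Protocol 2.2 states the matching objective as use of rescue and "changes in concurrent ITP therapy while receiving treatment with efgartigimod compared to placebo".

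SAP 4.1.2.3 item 7 supplies the derivation. The therapy start date is compared with the "target ADY of analysis visit corresponding to week 12) AND (dose > previous dose of the specific ITP therapy", followed by the same condition for frequency and then "OR new ITP therapy". The protocol endpoint mentions only dose and frequency; the counting of new starts comes from the SAP. Neither document gives a last day.

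SAP 3.5.2 is equally open at the far end: "New concurrent ITP therapy: started after first IMP dose date". SAP 2.2.1 says that medications are allocated to phases under 3.5.2, but that section classifies therapies only relative to the first dose.

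Protocol section 5 has concomitant medication recorded until the last trial activity. SAP 2.2.1 gives a 4-week follow-up phase only to patients who leave the study or do not roll over. For patients in that position, protocol 6.9 says that "usual treatment will be administered if required".

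**The concern.** Taken together, these rules let ITP care begun after study drug has stopped enter a table meant to describe escalation on treatment. The extra exposure is not shared equally. A rollover patient leaves this trial at week 24 and cannot contribute a follow-up start, whereas a patient who completes without rolling over can. Rollover and early exit both happen after randomisation and may differ by arm, so the comparison in the table could shift in either direction. The endpoint would then not answer its stated objective.

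**Working it through.** **Inputs.** SAP Table 3 (target days), SAP Table 2 (phase ends), protocol 5.5 (4-week follow-up). Days are nominal; the +2-day visit window is ignored. For rollover patients Table 2 ends the treatment phase at the End-of-Study date, which I take to be the End-of-Treatment visit.

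**Target days.** Table 3 gives target day = 29 + 7 × (week − 4).
- Week 23: 29 + 7 × 19 = 162, and week 24: 29 + 7 × 20 = 169. Both match Table 3.
- Week 12: 29 + 7 × 8 = 85.
- End of follow-up for a completer: 169 + 28 = 197.

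**Window under item 7 as written.**
- Rollover patient: 169 − 85 + 1 = 85 days.
- Completer who does not roll over: 197 − 85 + 1 = 113 days.
- Difference 28 days; 113 / 85 = 1.33, so 33% longer.

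**Early leavers.** A patient who exits on day d is followed to d + 28. This reaches day 85 only if d ≥ 57, the week 8 target day. An exit at week 9 (day 64) gives follow-up to day 92, so days 85 to 92 count: 8 days, all after trial exit. Patients who withdraw consent have no follow-up.

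**Illustration.** The documents give no rollover rate, so every rate here is assumed. Let p be the true proportion with an increase in the treatment phase, equal in both arms; a and b the shares of each arm entering follow-up; and q the chance that such a patient, not already counted, starts ITP therapy there. All entrants are assumed to reach day 85. The spurious difference is (1 − p) × q × (b − a).
- Low: p = 20%, q = 20%, a = 5%, b = 15%: 0.8 × 0.2 × 0.10 = 1.6 points.
- High: p = 10%, q = 50%, a = 15%, b = 30%: 0.9 × 0.5 × 0.15 = 6.75 points.
- With a = b the difference is 0, but both proportions are inflated. For a = b = 5% and p = 10%, 10% becomes 10.9% (q = 20%) to 12.25% (q = 50%).

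**With the end date.** Every completer has days 85 to 169, 85 days.

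**The case against.** The best counter-argument is that the SAP already excludes these starts. SAP 2.2.1 says that all events are allocated to phases, and SAP 2.2.3 restarts the relative day at the beginning of follow-up. A start in follow-up would then carry a day of about 1 to 30, below 85, and drop out. But the restart is stated for assessments, and 3.5.2 does not assign medications to a phase. On this reading the starts disappear by accident, and two programmers could produce different tables. The treatment-phase limit in SAP 4.1.2 does not settle it either, because it covers visits used for responses and time to response, not therapy start dates.

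Three stronger readings are tempting, and the documents do not support them.
- *The rescue rate (item 6) has the same flaw.* Its numerator carries no explicit phase limit, but protocol 6.8.4 and SAP 1.3 allow rescue only within the 24-week period. Treatment in follow-up is usual care, a different category.
- *The primary endpoint is exposed.* SAP 4.1.2.1 makes a patient with an intercurrent event a non-responder only if sustained response was not reached beforehand. A week 19–24 responder who starts therapy in follow-up stays a responder. The protocol's wording in 3.1 and 8.4.1 lacks that condition for therapy increases, but the SAP plans no analysis on it.
- *The number of miscounted patients can be estimated.* If 10–25% of 156 patients (16 to 39) entered follow-up and 25–50% of them started or raised therapy, that would be 4 to 19.5 patients, or 2.6 to 12.5 percentage points. This is an upper limit under assumed rates: it ignores patients already counted in weeks 12 to 24 and early leavers whose follow-up ends before day 85.

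**Conclusion.** The derivation is wrong as written for its stated objective. The firm result is the unequal window, 113 against 85 nominal days among completers, which needs no assumed rates. The 1.6 to 6.8 point difference is only an illustration; its direction depends on which arm has more patients entering follow-up, and it vanishes if the arms are equal.

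The consequence is limited. SAP 4.1.3 plans only a frequency tabulation for this endpoint (Table 14.2.6.1), with no test, and the endpoint is outside the alpha-controlled sequence. The intercurrent-event tabulation (Table 14.2.7.1) relies on concurrent-therapy definitions that also have no end date, so it can pick up follow-up starts too. The correction is still worth making, because it changes what a prespecified table counts.

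**What to change.** - In SAP 4.1.2.3 item 7, add: *and start date not later than the end of the treatment phase (Table 2), with days counted from first IMP dose*.
- In SAP 3.5.2, add the phase rule for medications that 2.2.1 refers to.
- Apply the same end date to the concurrent-therapy events tabulated as intercurrent events under 4.1.2.1 and 4.1.2.2.

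The phase end is already derived, so the cost is a few lines of SAP text and programming.

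The SAP should also state what this does not achieve. Under protocol 4.4.2, patients who stop study drug but stay in the trial continue weekly visits, and under Table 2 they remain in the treatment phase. Their later increases would still count. Early leavers would still have shorter windows. The change gives completers a common window, not a strictly on-drug one.

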### **Safety Evaluation**

- Evaluate the incidence and severity of AEs, AESIs, and SAEs.
- Evaluate vital signs, ECG, and laboratory assessments.

# 3.3. Exploratory Endpoint

argenx BVBA Confidential Page **42** of **162** 

### 4. INVESTIGATIONAL PLAN

## 4.1. Summary of Trial Design

#### **DESCRIPTION**

This is a phase 3, multicenter, randomized, double-blinded, placebo-controlled, parallel-group, up to 31-week trial to evaluate the efficacy, safety, and impact on QoL of efgartigimod 10 mg/kg IV treatment in adult patients with primary ITP.

The total maximum trial duration per patient is up to 31 weeks:

- a screening period of up to 2 weeks
- a treatment period of 24 weeks where all patients will receive IV infusions of efgartigimod 10 mg/kg or placebo
- End-of-Treatment visit 1 week after visit 24
- a follow-up period of 4 weeks

The target population are adult patients with persistent or chronic primary ITP, having an average platelet count of  $<30\times10^9$ /L, and at the start of the trial being on concurrent ITP treatment(s) and having received at least 1 prior therapy for ITP in the past or not being on treatment for ITP but having received at least 2 prior treatments for ITP. If patients are receiving concurrent ITP therapies at baseline, these therapies should have been maintained at a stable dose and dosing frequency for 4 weeks prior to randomization. As of week 12, the start or an increase in the dose and/or schedule of permitted concurrent ITP therapy is allowed for patients who have an "insufficient response" (ie, no platelet count of  $\ge 30\times10^9$ /L in any of the visits during the last 4 weeks). These patients will be considered as "non-responders" for the primary endpoint analysis.

After confirmation of eligibility, the patients enter a 24-week treatment period and will be randomized to receive 10 mg/kg IV of efgartigimod or placebo, weekly from visits 1 to 4 and then from visits 5 to 16 either weekly or q2w, adjusted according to their platelet counts. From visits 17 to 24, patients will be fixed on the dosing schedule they were receiving at visit 16 or at the last visit at which IMP was administered (ie, either weekly or q2w). Assessment of the dosing regimen as described in Section 5.4.1 will be applied.

Patients completing the 24-week trial period will perform the End-of-Treatment visit and can enter the open-label extension trial (ARGX-113-1803) to receive efgartigimed 10 mg/kg IV. The platelet counts from the ARGX-113-1801 trial will be taken into account to assess the dosing frequency in ARGX-113-1803.

Patients who complete the 24-week trial period but who do not enter the open-label extension trial ARGX-113-1803, or patients who discontinue the trial early, with the exception of

argenx BVBA Confidential Page 43 of 162

patients who withdraw their consent, will be followed for 4 weeks for ongoing safety and efficacy monitoring.

For patients who discontinue the trial early, all the assessments listed for the Early Discontinuation visit as specified in the schedule of assessments (SoA, Table 1), will be performed.

### SAMPLE SIZE AND STRATIFICATION

Approximately 117 patients with chronic ITP and up to 39 patients with persistent ITP will be randomized in a 2:1 ratio to receive efgartigimod or placebo, respectively. Recruitment will end when 117 patients with chronic ITP have been randomized.

Patients will be stratified according to the following factors:

- History of splenectomy (yes vs. no)
- Receiving concurrent ITP therapies at baseline (yes vs. no)

#### SCREENING AND TREATMENT

During the screening period (up to 2 weeks) the patient's eligibility for trial participation will be evaluated.

All eligible patients will be randomized to receive IV infusions of either efgartigimed 10 mg/kg body weight or matching placebo throughout the trial.

All patients will initially receive weekly IV infusions from visits 1 to 4.

Based on the platelet counts as of visit 2, the dosing frequency can be altered from visits 5 to 16 according to the following rules (the change in dosing frequency will occur at the current visit):

- Reduce from weekly to q2w in patients achieving platelet counts of ≥100×10^9/L for 3 out of 4 consecutive visits (the fourth visit being the current visit), and have a platelet count of ≥100×10^9/L at the last of these 4 visits
  - -OR-
  - 3 consecutive visits
- Increase from q2w to weekly in patients whose platelet counts drop below 100×10^9/L on 2 consecutive visits
  - -OR-
  - $<30\times10^9/L$  at 1 visit
  - -OR-

in patients who receive rescue therapy (see Section 6.8.4)

argenx BVBA Confidential Page 44 of 162

- Temporary withholding treatment
  - o for the reasons described in Section 4.5, IMP should be reintroduced once the investigator considers the undue risk to the patient has passed
  - o in patients with platelet counts greater than  $400 \times 10^9$ /L, IMP should be resumed at the 10 mg/kg q2w dose when the platelet count falls to fewer than  $150 \times 10^9$ /L
- Post-baseline platelet count can be performed within 1 day of the next procedure as per the SoA (both dosing and non-dosing visit), allowing the results to be incorporated into the criteria above.

From visits 17 to 24, the dosing frequency is fixed for each individual patient (ie, either weekly or q2w regimen), based on the regimen the patient was receiving at visit 16 or at the last visit at which IMP was administered.

Exceptions to the fixed dosing frequency are:

- Continued weekly dosing for patients requiring rescue therapy.
- Continued q2w dosing for patients resuming IMP when the platelet count falls to fewer than  $150 \times 10^9$ /L after having had platelet counts greater than  $400 \times 10^9$ /L.

